## **2.B. Significance and Relevance to Veterans' Health and the VA PACT Initiative**

This study will provide patient-reported FHL and patient activation information to PACT members to improve collaborative goal-setting in patients with treated but uncontrolled diabetes and ultimately, improve clinical and patient-centered outcomes.

**2.B.i. We will use an innovative strategy that brings together three elements to improve the quality and responsiveness of VA PACT care to the needs of over 1,000,000 Veterans with diabetes.** First, the study seeks PACT clinical team members' input on barriers and facilitators to the delivery of patient-reported FHL and activation measures to PACTs and then evaluates processes for implementing an innovative diabetes goal-setting intervention personalized to patients' activation and FHL levels across PACTs. Second, the study trains PACT members to use FHL and activation information to better personalize collaborative goal-setting. Most importantly, the study evaluates the clinical effectiveness of this personalized,

collaborative goal-setting intervention on clinical and patient-centered diabetes outcomes, relative to enhanced usual care (EUC).

**2.B.ii. Our protocol delivers FHL and activation measures at the point of care to personalize collaborative diabetes goal-setting-consistent with the PACT mission.** When delivered at the point of care, measures of FHL and activation can influence how PACT members engage in collaborative goal-setting. Considering patient-reported levels of FHL and activation allows for a personalized process of goal-setting, resulting in:

- more specific, personalized feedback shaped by their awareness of patients' activation and FHL,
- higher quality self-management goals and action plans, which in turn promote greater self-efficacy, and
- ultimately, better diabetes clinical and patient-centered outcomes.

This study uses a hybrid type 1 design in which the primary focus is on testing the effectiveness of personalized goal-setting versus enhanced usual care on diabetes outcomes (aim 2), while also collecting some implementation data. Our objective is to test the personalized collaborative goal-setting intervention with a randomized controlled trial (Phase 2) within the constraints of PACT workflows using real-world PACT members instead of research staff. The implementation aim (Phase 1) includes a formative evaluation intended to facilitate integration of the personalized goal-setting intervention within routine PACT workflows and a summative evaluation that measures aspects of implementation. Work on Phase 1 is already underway and is approved under the auspices of the Baylor College of Medicine IRB, the local IRB of record for the Michael E. DeBakey VA Medical Center in Houston, TX.

### 3.0 Objectives

The overall goals of this hybrid type I effectiveness/implementation trial are to 1) evaluate the process of implementing a collaborative (i.e., patient and PACT member) goal-setting intervention personalized to patient activation and FHL (i.e., Empowering Patients in Chronic Care [EPIC]) into routine PACT care; and 2) test the effectiveness of this intervention relative to enhanced usual care. In Phase 1(Aim 1), we used the Promoting Action on Research in Health Services (PARIHS) framework to evaluate the feasibility of potential implementation processes into routine PACT care. In Phase 2 (Aim 2), we will assess the effect of delivering personalized goal-setting on clinical (e.g., HbA1c) and patient-centered (e.g., diabetes-related distress) outcomes among Veterans with uncontrolled diabetes. We anticipate that delivering personalized goal-setting involving patients and their PACTs will lead to improvements in diabetes care.

**3.B. Specific Aim 1: Assessed effective processes for and costs associated with implementation of a collaborative diabetes goal-setting intervention personalized to patient activation and FHL (i.e., EPIC) into the routine workflows of PACTs.**

H1: Formative measures within the PARIHS framework (evidence, context, facilitation) will be associated with implementation of EPIC (defined by reach, adoption, cost effectiveness, and fidelity measures) into routine PACT care.

**3.C. Specific Aim 2:** Evaluate the effectiveness of delivering collaborative goal-setting personalized to patient activation and FHL on clinical (HbA1c) and patient-centered (Diabetes Distress Scale) outcomes among eligible patients.

H2: Patients receiving collaborative goal-setting personalized to activation and FHL levels will have significant improvements in a) HbA1c and b) Diabetes Distress Scale levels, respectively, post-intervention compared with patients receiving enhanced usual care.

H3: Patients receiving collaborative goal-setting personalized to activation and FHL levels will maintain significant improvements in a) HbA1c and b) Diabetes Distress Scale levels at 1-year follow-up, respectively, compared with patients receiving enhanced usual care.

## **4.0 Resources and Personnel**

### **4.A. Location of Research, Phase 1 and Phase 2**

All data analysis for Phase 1 and Phase 2 will occur at the Houston VA IQuEST (see § D 5.6 Data analysis)

**4.A.ii. Services Provided by Contractors**

Not applicable: no contractors were involved in Phase 1 or will be involved in Phase 2.

**4.A.iii. Memoranda of Understanding (MOU) or Data Use Agreements (DUA)**

Phase 1 required no DUA or MOU. For any databases used in Phase 2 that require Data Use Agreements or Memoranda of Understanding, we will complete all required DUA or MOU paperwork.

Databases that require a DUA include:

- Corporate Data Warehouse (CDW): we will complete DUA to access VINCI

In addition, if a DUA or MOU is needed for use of other databases controlled by VA partners, we will complete that paperwork as well, prior to using the database for research.

## 5.0 Study Procedures

[figure not shown]
### 5.1 Study Design

#### 5.1.A. Overall Study Design

The study will be conducted over four years in two phases. In Phase 1, we implemented our personalized collaborative goal-setting intervention into routine VISN 12 PACT care. To facilitate implementation, we conducted a formative evaluation of VISN 12 PACTs guided by the PARIHS framework. This method of evaluation consisted of key informant interviews with providers, staff, and facility leadership to identify: a) how well PACT members embrace our training/fidelity program for personalized goal-setting (PARIHS evidence), b) how the intervention sessions can be best embedded into routine workflows of PACT at a local level (PARIHS context), and c) local PACT members to assist with recruitment (PARIHS facilitation) of VA staff to conduct the intervention. Phase 1 began during the first year of the study. In the final year of the study, we will also conduct a summative evaluation of overall intervention implementation success based on the RE-AIM measures (see table 5 below) of reach, adoption, and implementation (i.e., cost-effectiveness and fidelity to intervention).

In Phase 2, (see Figure 2) we will conduct a randomized controlled clinical trial to assess the effectiveness of personalized goal-setting in improving clinical and patient-centered outcomes compared with EUC. The unit of randomization will be at the patient level with patients enrolled into the personalized goal-setting intervention (EPIC) versus EUC. Outcome assessments will be conducted at baseline, immediately post-intervention (4 months), and 10 months post-randomization after a maintenance phase.

**Figure 2: Empowering Patients in Chronic Care (EPIC) Study Design (Effectiveness Phase)**

With the assistance of PACT members and using strategies identified in Phase 1 (formative evaluation), we recruited VA staff who regularly participate in diabetes care to serve as group leaders and individual session providers for the intervention. In Phase 2, we will also recruit and randomize Veterans across eligible facilities to participate in our trial.

Patient-participants will be recruited from PACT patient panels. Patient panels will be screened for eligibility criteria, and all eligible patients will be approached for informed consent to participate in the study using an opt-out approach and a structured telephone screening and recruitment process.

The study intervention, EPIC (see Figure 3), will consist of six sessions conducted over a maximum of 6 months. Each session will include a group visit followed by a one-on-one personalized goal-setting visit. The personalized goal-setting sessions will incorporate FHL and activation information, allowing the designated study team member to collaborate with patients at their desired levels of engagement to develop diabetes self-management goals.

Patients enrolled in the EPIC intervention will participate in a group session, followed by an individual, collaborative goal setting session. Group sessions will be run by a group leader, a VA staff member who is a regular provider of diabetes care in VISN12. The group leader will be trained to use the EPIC protocol to empower patients in diabetes goal-setting, action planning, and proactive communication with PACT members.

Following the group sessions, participants will receive individual, collaborative goal-setting sessions with an individual session provider, another VA staff member who is a regular provider of diabetes care in VISN12, who is trained by the study staff to lead these goal-setting sessions. Individual sessions will follow the group sessions at a mutually convenient time. The individual session provider will be trained to a) conduct collaborative goal-setting for diabetes self-management and b) understand how to use measures of patient activation and FHL personalized to each patient-participant to enhance the collaborative goal-setting process. Designated VISN12 staffers undergoing EPIC training will be consented as research subjects and must complete an intervention fidelity assessment prior to qualification for the active intervention (§ 5.1.F.).

Patients enrolled in the EUC arm will receive routine PACT visits and “enhanced usual care” (EUC). Patients randomized to EUC will be referred to the PACT RN Care Manager for diabetes management, and will also receive a packet of educational materials regarding diabetes management, including a letter delineating the diabetes management resources available at their facility. The PACT RN will be directed to provide care as usual. Patients

enrolled in EUC will not receive group or individual goal-setting information defined by the EPIC protocol and their PACT teamlets will not receive personalized information about patient activation or FHL.

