have experience with goal-setting and action-planning as a part of the standard diabetes care that they provide. These EPIC individual session providers will undergo a standardized training program specific to EPIC conducted by the research staff (§ 5.1.F.). Each staff member will have time dedicated to complete our training program for the EPIC intervention. Individual session providers will participate in fidelity assessments to ensure internal validity (§ 5.1.F.). The individual session providers of the EPIC goal-setting intervention were identified during Phase 1 at each facility. Dietitians, pharmacists, diabetes educators and health promotion disease prevention (HPDP) specialists were identified by network PACT leadership as being ideally suited to conduct the intervention. They routinely conduct individual counseling sessions and are trained in motivational interviewing, which will enhance their effectiveness as participants in the EPIC intervention. Given the implementation focus of the research and shifting staffing patterns at each facility, all interested VA staff members who provide diabetes counseling as part of their regular job duties will be eligible to participate as individual session providers.

Prior to training in Phase 2, we will consent and enroll the individual session providers as research subjects. Individual session providers will be consented as research subjects specifically to collect implementation data on the EPIC intervention. We expect to enroll 3-7 individual session providers at each facility, for a maximum total of 34 subjects.

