conducting the one-on-one sessions (e.g., in-person right after group sessions, in-person at another time, telephone based). Each individual session provider will have the freedom to choose the option that best fits their usual workflow and scheduling process. In preparation for one-on-one sessions, the session provider will receive information on their patients' activation and FHL levels at the start of the intervention. We used the key informant interviews from Phase 1 to inform our process for delivering these patient-reported measures to participating VA staff. In particular, we developed a succinct and actionable format for presenting these data and will train the individual session providers on how to integrate the information into goal-setting (§ 5.1.F.) The individual session provider will use this information to better personalize the development of high quality, collaborative goals and action plans. At the conclusion of the individual session, the provider will convey the specified goals and action plans discussed, as well as any medication-related or other issues raised by patient participants to the PACT teamlet via a CPRS note. Given the importance of medication management in the original EPIC study, we developed standardized procedures in Phase 1 for medication management, including medication reconciliation, dose titration, and addition/initiation of alternate medications. The goal is for the individual session provider to work with the Veteran in the course of the individual goal-setting session to resolve common issues regarding medications, communicate those issues to the prescribing PACT clinician, and subsequently ensure that modifications to medication regimens are implemented by patients.

Research staff will contact EPIC patient-participants to schedule post-intervention and post-maintenance follow up assessments and HbA1c collection.

**5.1.E.iv. Procedures for handling EUC.** The full EUC intervention includes: 1) a referral to the PACT RN Care Manager, 2) a packet of educational materials about diabetes management (Attachment 5), and 3) a letter from the research staff delineating the diabetes management resources available at their facility and encouraging them to speak to their PACT teamlet about these resources (Attachment 6).

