#### **5.5.B. Data Collection Strategy § 5.1.H.**

#### **5.5.C. Study Variables § 5.1.I.**

### **5.6 Data Analysis**

#### **5.6.A. Sample Size Calculation/Sample size determination**

Sample size is calculated according to the estimated intervention effect size at post-intervention. We then estimate power to detect treatment effects at the post-maintenance (10-month) follow-up as well as power to detect treatment differences in linear change across the three time points for a 3-level cluster-randomized trial with repeated assessments. We will adjust models for baseline covariates of study patients. All tests will be two-sided with an alpha of 0.05. In our recent RCT, differences in HbA1c change between EPIC versus enhanced group education indicated medium treatment effects at post-treatment and at 1-year (Cohen's  $d = 0.48$  and  $0.42$ , respectively). A similar trial revealed a treatment difference between a glucose self-monitoring protocol and an active control group in DDS scores that correspond to large effects of treatment at 1-year (all pre-post  $d$ s  $> 0.80$ ). To capture treatment effects for both clinical and patient centered outcomes in this implementation trial, a conservative small-to-medium effect size of  $d = 0.40$  (which is 16.67% smaller than the effect found for HbA1c in the prior trial) was used to calculate sample size. Assuming no intra-class correlation (ICC) within

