PACTs, 100 patients in each treatment arm (i.e., EPIC and EUC) will allow for 80% power to detect small-to-medium effects and 98% power to detect medium effects ( $d = 0.50$ ). To account for the dependency among patients within a PACT, the Design Effect (Deff) was applied, following the approach of Schnurr et al. The sample size was inflated using the formula,  $Deff = 1 + (n-1)\rho$ , where  $n$  is the average number of patients per PACT and  $\rho$  is the ICC for PACTs. In our preliminary work, we identified an ICC for PACTs of 0.0183, an average of 27 eligible patients per PACT, and expect that an average of 12 patients per PACT will participate, which yields  $Deff = 1 + (12-1) * 0.0183 = 1.2013$ . Applying this adjustment, the minimum number of patients in the clustered design is  $100 \times 1.2013 = 120$  in each treatment group. Further adjusting for a maximum of 15% attrition, 142 patients will be recruited for each treatment group (total  $N = 284$ ). Therefore, the minimum number of PACTs to be sampled for this nested analysis is technically 11.8, (i.e.,  $142/12$ ), which will be rounded up to 24 PACTS. This is highly feasible, representing just 32.5% of the total number of PACTs (75) at all study sites. Treatment group effect sizes as small as  $d = .40$  can be detected with 80% power at 1-year given a total of 284 patients (an average of approximately 12 patients randomized to either EPIC or EUC from within 24 PACTs sampled), even after accounting for maximum attrition and estimated dependency within PACTs. A sample size of 284 participants is adequate for repeated measures analyses as well. Optimal design software estimated power to detect treatment group differences in linear change across all three assessments. Prior data indicated a main effect of treatment (EPIC versus enhanced group education) for linear change in HbA1c of 0.20, and between – and within – PACT variance in linear change of 0.018 and 0.206, respectively. These values indicate a small-to-medium between-groups effect size of 0.42. A total of 284 participants allows for 80% power to detect a slightly larger effect size ( $\delta = .53$ ) for repeated measures analyses of linear change over time. Furthermore, there is 98% power to detect a medium effect size of  $\delta = .75$ .

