Specific Aim 2: The distributional nature of all variables will be assessed, and nonparametric tests (e.g., Fisher's Exact Test; Mann-Whitney test), data transformations (e.g., log linear), or other alternate methods (e.g., weighted least squares regressions) will be conducted where appropriate. First, we will compare baseline demographic, clinical, and patient-centered variables (including medication use) between EPIC and EUC with chi-square and independent samples t-tests. Variables with p-values  $< 0.25$  will be included as control variables or propensity scores in subsequent models. We will then compare baseline demographic, clinical, and patient-centered variables between those who complete the study and those who do not using chi-square and independent samples t-tests. Outcome analyses at both post-intervention and post-maintenance will be intention-to-treat and will use the multiple imputation procedures Proc MI and MINANALYZE in SAS Version 9.3 to estimate missing observations. We will evaluate the degree of dependency between patients within a given group session, between patients in a given PACT, and between PACTs within each of the five sites (by examining Intra Class Coefficients). It is likely that significant dependency will exist, and if so, we will accordingly take these into account in analyses (i.e., patients will be nested within PACTs which will in turn be nested within sites). Random regression methods using SAS Proc Mixed will be employed to account for clustering of data.

5.6.C.i. H2 Analyses (Effectiveness) We will employ Analysis of Covariance (ANCOVA) to examine treatment differences in outcomes immediately post-intervention (at 4 months). We will conduct two models: one with HbA1c at post-intervention as the outcome and one with DDS at post-intervention as the outcome. Models will include treatment group (i.e., EPIC versus EUC) as a predictor and respective HbA1c and DDS baseline scores and any demographic,

clinical, or patient-centered variables that differed between the study arms at baseline as covariates. We will calculate treatment effect sizes immediately post-intervention.

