5.6.C.ii. H3 Analyses (Maintenance) Analyses for examination of maintenance of treatment effects will be similar to those for immediate treatment effects post-intervention. We will again employ ANCOVA to examine treatment differences in outcomes at the post-maintenance (10-month) assessment. We will conduct two models: one with HbA1c at 10-months as the outcome and one with DDS at 10-months as the outcome. Models will include treatment group (EPIC versus EUC) as a predictor and respective HbA1c and DDS post-intervention scores and any demographic, clinical, or patient-centered variables that differed between the study arms at baseline as covariates. We will calculate treatment effect sizes at the 10-month assessment.

5.6.C.iii. Exploratory Analyses (Implementation and Effectiveness) We will use a mixed-model approach to conduct separate repeated-measures analyses for HbA1c and DDS simultaneously using all three assessment time points. We will employ growth curve analyses using SAS Proc Mixed to examine overall group differences in improvements or decrements in outcomes over the year, maximize participant data, and account for dependency between patients within a given group session, PACT, and site. Conditional models will contain fixed terms for the intercept, treatment (EPIC or EUC), assessment time period, treatment by time period interaction, and previously identified variables that differ between treatment groups. Modeled random effects will include between-patient variation in baseline scores (i.e., the intercept where baseline assessments are scored 0) and variation in the slopes for time. With three assessments, the focus will initially be on linear patterns of change, although we will evaluate the relative fit of a quadratic pattern of change using the likelihood ratio test. These analyses will allow us to examine the immediate impact of treatment at post-intervention as well as retention, improvement, or decay in outcomes post-maintenance period. The treatment effect will assess differences between the two groups at baseline, the fixed effect of time will measure the average change over time in the outcome (collapsing across the two treatment groups), and the time by treatment interaction will indicate whether change over time (in slopes) differs between EPIC and EUC.

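### Individual session providers treat EPIC patients only, yet provider is missing from the clustering sources, the H2/H3 models and the design effect; standard errors will be too small if provider effects exist and providers serve more than one group.

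*Combined protocol and SAP*

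**What the plan says.** **Delivery.** Section 5.1.A gives EPIC patients six group sessions, each followed by a one-on-one session: "participants will receive individual, collaborative goal-setting sessions with an individual session provider, another VA staff member". The activation and health-literacy information is used in these one-on-one sessions, and the provider also works through medication issues with the patient (5.1.B, 5.1.E.iii). On mode of delivery, in person or by telephone, 5.1.E.iii says: "Each individual session provider will have the freedom to choose the option that best fits their usual workflow". EUC patients receive no EPIC individual sessions.

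**Size of the pool.** Section 5.1.D.ii: "We expect to enroll 3-7 individual session providers at each facility", with a ceiling of 34. Section 5.1.B uses 34 for group leaders and individual providers taken together. Section 5.2.A gives 3-6 individual providers per facility within a ceiling of 40 staff.

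**Analysis.** The Aim 2 text in 5.6.C begins: "We will evaluate the degree of dependency between patients within a given group session, between patients in a given PACT, and between PACTs", the last of these within five sites. It then says that dependency will be taken into account if it is found, and describes the structure as patients in PACTs in sites. Group session is not part of that stated nesting. The H2 and H3 ANCOVAs list treatment, a prior score and covariates. The exploratory growth model is meant to "account for dependency between patients within a given group session, PACT, and site". The design effect in 5.6.A uses a PACT ICC only. Individual session provider is named in none of these places.

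**The concern.** Patients who share a provider may share part of their treatment effect. Providers come from several disciplines (dietitians, pharmacists, educators, health promotion specialists), choose their own mode of delivery, and act on medication issues that could move HbA1c directly. Any such correlation exists in the EPIC arm only. PACTs and sites contain patients from both arms, so a random intercept for either does not represent it.

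A group-session term represents it only as far as a provider's patients sit in the same group. A provider who sees patients from several groups induces correlation between those groups, which a group term treats as independent. The standard error of EPIC minus EUC for HbA1c and Diabetes Distress Scale is then too small, and the stated level ("All tests will be two-sided with an alpha of 0.05") is not held.

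**Working it through.** **1. The plan's own figure.** Section 5.6.A uses "a conservative small-to-medium effect size of" d = 0.40 and says that "100 patients in each treatment arm (i.e., EPIC and EUC) will allow for 80% power to detect small-to-medium effects".
- n per arm = 2(1.960 + 0.842)²/0.40² = 98.1, so 99 (stated: 100).
- Design effect = 1 + (12 - 1) × 0.0183 = 1.2013, and 100 × 1.2013 = 120.
- 120/0.85 = 141.2, so 142 per arm and 284 in total.

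The stated sample size reproduces. The only clustering in it is by PACT.

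**2. Groups and providers.** Groups hold 5-8 patients (5.1.E.iii), so 142 EPIC patients form 142/8 = 17.8 to 142/5 = 28.4 groups, about 18-28.
- At 34 providers the mean caseload is 142/34 = 4.2. There are at least as many providers as groups, so each provider could stay within one group.
- At 15 providers (three at each of five sites) the mean caseload is 142/15 = 9.5. Fifteen is fewer than 18, and every group needs at least one provider, so some providers must serve several groups.
- The enrolment split in 0.0.3 is 200 Jesse Brown, 160 Hines and 68 Houston plus Lovell, of 428. Applied to 142 this gives 66.4, 53.1 and 22.6 EPIC patients. With three providers at each of these four facilities the caseloads are 22.1, 17.7 and 3.8. The size-weighted mean is (66.4 × 22.1 + 53.1 × 17.7 + 22.6 × 3.8)/142 = 17.5. Counting the Crown Point clinic as a separate facility with its own three providers lowers it to 12.4.

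**3. Formulas.** These use a normal approximation and equal caseloads within site. The analysed number is 120 per arm, and m is the caseload × 0.85 for attrition.
- True EPIC-arm inflation: D = 1 + (m - 1)ρ, with ρ the provider ICC.
- Inflation carried by a group term: D_g = 1 + (min(m, 5.5) - 1)ρ. The 5.5 is an assumed average group of 6.5 × 0.85.
- Model SE over true SE: √[(D_g + 1)/(D + 1)], or √[2/(D + 1)] with no EPIC-side term.
- Type I error = 2[1 - Φ(1.96 × ratio)].

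Example, caseload 9.5 and ρ = 0.05: m = 8.075, D = 1.354, D_g = 1.226. The ratio is √(2.226/2.354) = 0.973, giving 5.7%. With no EPIC-side term it is √(2/2.354) = 0.922, giving 7.1%.

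**4. Results for ρ = 0.02 / 0.05 / 0.10.** The documents give no provider ICC, so this range is an assumption.

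| Patients per provider | Type I error, group session modelled | Type I error, no EPIC-side term |
|---|---|---|
| 4.2 (providers within groups) | 5.0 / 5.0 / 5.0% | 5.3 / 5.7 / 6.5% |
| 9.5 | 5.3 / 5.7 / 6.2% | 5.8 / 7.1 / 9.2% |
| 12.5 | 5.6 / 6.3 / 7.5% | 6.1 / 7.8 / 10.7% |
| 17.5 | 6.0 / 7.5 / 9.5% | 6.6 / 9.1 / 13.2% |

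The middle column assumes that patients in one group share a provider. If groups are split over providers who each serve several groups, the group term carries less and the error moves towards the right-hand column.

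**5. Power once provider is modelled.** Power = Φ(0.40/√[(D + 1)/120] - 1.96), with no PACT inflation. It is 85 / 82 / 76% at caseload 9.5 and 83 / 76 / 66% at 17.5. With no clustering at all it would be Φ(0.40 × √60 - 1.96) = 87%.

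**The case against.** The strongest reply is that the plan already recognises EPIC-side clustering by naming group session, and that nothing shows a provider effect beyond it. The only ICC in the documents is 0.0183, for PACT. A provider ICC of that size would put the result near the 0.02 entries, 5.3% at 9.5 patients per provider with group session modelled. The plan also limits provider variation: standardized training, role-play repeated until fidelity is acceptable (5.1.G.a), and a menu of only two or three delivery modes. One person may be both leader and provider (5.1.B), leaders may help with goals (5.1.E.i), and the one-on-one may directly follow the group. Provider and group may therefore largely coincide.

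Much of this stands. It makes the size uncertain and allows it to be nil. It does not close the gap, because the documents give no rule tying providers to groups, and at the lower staffing figures some providers must span groups.

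A reader might infer that the standard errors are certainly too small even with group session modelled, or that error of 7% or more at 9.5 patients per provider applies in that case. The documents support neither. The first needs a positive ICC and multi-group caseloads. The second holds only when no EPIC-side term is fitted. Nor do they single out the one-on-one session as the only effective component: 5.1.E describes group training and individual support together.

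**Conclusion.** The omission is real; its effect is conditional. Provider is a plausible source of correlation in one arm only, and no part of the analysis or sample size accounts for it. With group session modelled, the EPIC versus EUC standard error is correct if each provider works within one group. Over the assumed ICC range of 0.02-0.10 it is about 1-5% too small at 9.5 patients per provider and about 4-15% too small at a size-weighted 17.5. Type I error then runs from 5.0% to about 9.5%, and the top value needs minimum staffing at four facilities and the highest assumed ICC.

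The larger exposure is in 5.6.C itself: the stated nesting leaves out group session, and dependency is modelled only if found. If PACT-within-site is all that is fitted, error is about 5.8-9.2% at 9.5 patients per provider. All figures assume equal caseloads within site; unequal caseloads would raise them. The point merits a change to the analysis text before unblinding, but does not show that the trial's conclusions would be wrong.

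**What to change.** In 5.6.C, for H2, H3 and the growth model:
- Add individual session provider to the clustering sources. Prespecify a random effect for it in the EPIC arm only, alongside an EPIC-only effect for group session, with each EUC patient as their own cluster.
- Keep both terms whatever a significance test shows, with Kenward-Roger or Satterthwaite degrees of freedom.
- State in advance which term is simplified first if the model does not converge. Provider, group, PACT and site are a heavy load for about 120 analysed EPIC patients.
- For the intention-to-treat analysis, assign each EPIC patient to the provider scheduled for the first one-on-one session, so that non-attenders stay in. Section 5.5.A.i allows for more than one provider per patient, so add a crossed or multiple-membership model as a sensitivity analysis.

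Record the provider at every one-on-one session. Session notes in the medical record (5.1.E.iii) should make this recoverable, but the fidelity tracking in 5.1.F.iii counts sessions, not who delivered them. In 5.6.A, state an assumed provider ICC and caseload, and reconcile the provider counts in 5.1.B, 5.1.D.ii and 5.2.A.

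The cost is SAP wording, one recorded field and somewhat wider intervals. Power may fall below the stated 80%: about 76% at 9.5 patients per provider and ICC 0.10, before any PACT inflation.
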